6.7 Protocol Deviations

Protocol deviations will be summarized by classification [major/minor], study site and coded deviation term.

7. EFFICACY EVALUATION

The analysis of efficacy endpoints will be performed on the FAS as well as on the PPAS with the analysis on FAS considered the primary analysis.

7.1 Analysis of Primary Efficacy Outcome Measure

There is no primary efficacy outcome measure in this study.

7.2 Analysis of Secondary Efficacy Outcome Measure

7.2.1 Treatment of Bleeding Episodes

Summary statistics will be provided for the overall hemostatic efficacy rating at resolution of bleed as well as for the number of infusions per bleeding episode. These tables will be also presented by bleeding site (joint/non-joint), cause (spontaneous/injury) and severity (minor, moderate, major, and life/limb-threatening). These subgroup analyses will be performed on the FAS only.

As a sensitivity analysis to the assumption of independency between bleeds within the same subject, these summary tables will be also created with the assessment of the first bleed within a specific treatment regimen for each subject. This sensitivity analysis will be performed on the FAS only (and not by bleeding site, cause and severity).

Bleeding episodes, for which any hemostatic product other than BAX326 had to be used, will not be considered.

These tables will be created by treatment regimen as well as for all treatment regimens together.

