### **8.6.3 Description of Treatment**

All subjects will receive exclusively BAX326.

The treatment with BAX326 will be at the discretion of the investigator and will consist of either prophylaxis or on-demand. Newly recruited subjects will receive prophylactic treatment only.

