**Note:**

**It is critical to inform the subject that 'resolution of bleed' means 'cessation of bleed' and not 'cessation of all bleed-related symptoms'.**

- Type and number of analgesics required
- Overall clinical efficacy rating according to the rating scale as described in [Table 11.3-1](#) at resolution of bleed.

Table 11.3-1 Rating Scale for Treatment of Bleeding Episodes	
Excellent	Full relief of pain and cessation of objective signs of bleeding (eg, swelling, tenderness, and decreased range of motion in the case of musculoskeletal hemorrhage) after a single infusion. No additional infusion is required for the control of bleeding. Administration of further infusions to maintain hemostasis would not affect this scoring.
Good	Definite pain relief and/or improvement in signs of bleeding after a single infusion. Possibly requires more than 1 infusion for complete resolution.
Fair	Probable and/or slight relief of pain and slight improvement in signs of bleeding after a single infusion. Required more than 1 infusion for complete resolution.
None	No improvement or condition worsens.

If a bleed occurs following resolution of the bleed, it will be considered to be a 'new' bleed and recorded accordingly.

Subjects will resume their prophylactic treatment regimen the next scheduled day after the last therapeutic infusion for the treatment of a bleeding episode.

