Details pertaining to all home treatments for each bleed, including response to treatment, will be recorded by study subjects or the subject's legal representative in subject diaries provided by the study sponsor. At each study visit the investigator will review together with the subject the response to treatment and evaluate the hemostatic efficacy rating. Any inconsistency between the efficacy rating and the number of infusions required to treat a bleeding episode, or a response to treatment rated as "none" must be immediately clarified. If two or more responses to treatment are rated with "fair", the investigator may re-evaluate the dosing regimen, and the time from bleeding onset to start of treatment. In case more than one infusion was given to treat a bleeding episode, but the treatment was rated with "excellent", information should be provided about the severity of the bleeding episode and/or whether additional infusions were given to maintain hemostasis. If infusions were given to maintain hemostasis after resolution of bleed, this should be recorded accordingly in the eCRF. **It is important to clearly indicate after which infusion the bleed stopped.** This may not necessarily coincide with the cessation of objective signs of bleeding, such as pain or swelling, since the absorption of blood would still be ongoing. Particularly in the case of severe hemophilic arthropathy and/or previous

joint surgery combined with severe bleeds, it is more difficult to define exactly the time point of the cessation of the bleed. If pain persists despite several infusions of BAX326, the presence of a bleed should be verified. It may become necessary to re-discuss the rating with the subject to ensure that the Rating Scale is fully understood. Cases of bleeding episodes requiring only one infusion but with a response to treatment rated with “fair” should also be evaluated.

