If, at any time during the course of the study, a subject’s bleeding episode does not adequately respond to BAX326 therapy, he/she will be evaluated for the presence of inhibitory or total binding antibodies to FIX and clinically managed at the discretion of the investigator (see Section 12.7.1). In addition, AEs and the details of concomitant medication use coincident with the treatment of all acute bleeds will be recorded. Note that bleeding episodes are not to be reported as AEs (Section 12.3). Any non-study FIX therapy or hemostatic product use administered for a bleeding event will be recorded on the appropriate section of the subject’s diary and the eCRF. The use of a FIX concentrate other than BAX326 will disqualify the subject from further participation in the study.

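### SAP 7.2.1 drops bleeds that needed another hemostatic product from the rating and infusion tables, and no planned output counts them or shows the rating with them kept

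*SAP*

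**What the plan says.** SAP Section 7.2.1 plans two summaries of bleed treatment: the overall hemostatic efficacy rating at resolution, and the number of infusions per bleed. It then restricts which bleeds enter: "Bleeding episodes, for which any hemostatic product other than BAX326 had to be used, will not be considered". SAP Section 7 runs efficacy on both the FAS and the PPAS, and the restriction is not confined to either set. The one sensitivity analysis in Section 7.2.1 addresses dependence between bleeds in the same subject: "these summary tables will be also created with the assessment of the first bleed within a specific treatment regimen for each subject".

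Protocol Section 14.3.2.1 summarizes the same outcomes and states no exclusion of bleeds. Protocol Section 11.3 deals with the underlying events. It requires an antibody work-up when a subject's bleed "does not adequately respond to BAX326 therapy, he/she will be evaluated". It also says "Any non-study FIX therapy or hemostatic product use administered for a bleeding event will be recorded", and adds "The use of a FIX concentrate other than BAX326 will disqualify the subject from further participation in the study". That last sentence ends the subject's further participation; it does not say that the bleed is discarded. Protocol Section 14.2 keeps data through the day of discontinuation. The rating scale in Protocol Table 11.3-1 already has a bottom category, None, defined as "No improvement or condition worsens".

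**The concern.** Whether another product had to be used normally becomes known only after treatment of the bleed has begun, so the rule selects bleeds on a post-treatment event. That event is plausibly related to the outcome: Protocol Section 11.3 treats inadequate response and the recording of other products in the same paragraph. If some removed bleeds are non-responses, the denominator loses failures and the excellent/good percentage rises.

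Not every removed bleed would be a failure. The wording also covers bleeds in which another product was used only as an adjunct, and bleeds never given BAX326. The SAP does not define hemostatic product, so these groups are not separated. The effect on infusions per bleed can go either way.

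What is at stake is one secondary, descriptive result in an uncontrolled study. Without a count and a result that keeps these bleeds, a reader of the report cannot tell whether the exclusion mattered.

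**Working it through.** **Text check.** Places where the rule, or a count of the bleeds it removes, could have appeared:

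- Protocol Section 14.3.2.1: no exclusion of bleeds.
- SAP Section 5.5: four listed changes (missing-data techniques, added analysis sets, non-compartmental PK, IR at baseline and end of study only). The bleed rule is not among them.
- SAP Section 5.2: documents excluded data only where considered spurious.
- SAP Section 6.1: lists discontinued subjects and subjects left out of data sets, not bleeds.
- SAP Section 6.5: lists other hemostatic products for the FAS, with no stated link to a bleed and no count.
- SAP Sections 7.2.2 and 7.2.3: do not repeat the rule, so bleed counts may differ between tables without explanation.

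**Scale.** The plan states no figure to reproduce, and the documents give no number of affected bleeds. The pivotal-study results in Protocol Section 6.4.1 serve as a yardstick only: 249 bleeds, 96.0% rated excellent or good, 84.7% controlled with 1–2 infusions. The documents do not say whether those results used the same exclusion.

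Counts: 0.960 × 249 = 239.04, so 239/249 = 95.98%. 0.847 × 249 = 210.9, so 211/249 = 84.74%.

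Let k be the assumed number of removed bleeds, treating the 249 as those retained. If every removed bleed is a non-response, the figure with them kept is 239/(249 + k). If every one is rated excellent/good, it is (239 + k)/(249 + k).

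| k | all non-responses | points below 95.98% | all excellent/good |
|---|---|---|---|
| 1 | 239/250 = 95.60% | 0.38 | 240/250 = 96.00% |
| 3 | 239/252 = 94.84% | 1.14 | 242/252 = 96.03% |
| 5 | 239/254 = 94.09% | 1.89 | 244/254 = 96.06% |
| 12 | 239/261 = 91.57% | 4.41 | 251/261 = 96.17% |

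Mixed case: five removed, two of them non-responses, gives 242/254 = 95.28%.

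For control with 1–2 infusions, the range is 211/(249 + k) to (211 + k)/(249 + k): 84.40–84.80%, 83.73–84.92%, 83.07–85.04% and 80.84–85.44% for k = 1, 3, 5 and 12.

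**Larger base.** This study runs longer than the pivotal study, so 249 may be too few bleeds. Protocol Section 6.5 gives 82 subjects in this study at the 2013 cut-off, and Protocol Section 6.4.1 gives a mean ABR of 4.20 on prophylaxis. Assuming two years each at that rate: 82 × 2 × 4.20 = 688.8, about 689 bleeds. Then 0.96 × 689 = 661.4, so 661/689 = 95.94%. Three non-responses give 661/692 = 95.52%, a fall of 0.42 points; twelve give 661/701 = 94.29%, a fall of 1.64 points.

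**The case against.** The strongest defence is that the rule fits the aim. The outcome is the efficacy of the study product, and Protocol Section 8.6.3 says "All subjects will receive exclusively BAX326". A rating at resolution after a second product does not isolate BAX326, and a BAX326 infusion count cut short by another product would look too low. This stands, and it is why the exclusion can remain as one presentation. It does not explain why the number removed goes unreported.

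A reader might infer that leaving the rule out of SAP Section 5.5 shows an undisclosed departure from the protocol. The documents do not support that. The protocol is silent on which bleeds are evaluable, the rule is openly written in the section it governs, and SAP Section 7.2.2 likewise adds rules (a three-month minimum, and removal of surgery and bleeding periods) that Section 5.5 does not list.

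A reader might also infer that failures vanish from the report. That goes too far. Some would leave a trace in the listing of other products, the discontinuation listing or the antibody table. Protocol Section 12.1.1 has failure of expected pharmacological action treated as an AE, although it excludes bleeds themselves from AEs, so coverage there is uncertain. None of these outputs counts excluded bleeds or restores them to a denominator.

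Finally, it is fair to object to any remedy that sorts bleeds into BAX326 failure and adjunct use. Protocol Section 11.3 asks sites to record which infusion stopped the bleed ("It is important to clearly indicate after which infusion the bleed stopped") and that another product was used, but it does not ask for the reason. Sorting would bring judgement into an open-label study. The remedy below avoids it.

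**Conclusion.** The point holds as a reporting gap with a known possible direction and an unknown size. The rule can overstate the excellent/good share if the removed bleeds do worse than those retained. If none of them was a non-response, the share is unchanged or understated by at most 0.18 points for up to 12 bleeds on the pivotal base.

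The number of affected bleeds is probably small, because Protocol Section 10.4 bars other FIX concentrates, and it may be zero. The tempting stronger reading, that the result is overstated by more than one point, is not supported: it needs at least three non-responses on a 249-bleed base taken from a shorter study. On the assumed 689-bleed base the same three move the figure by about 0.4 points. All values of k, the two-year duration and the transfer of the pivotal rates are assumptions.

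The first-bleed analysis does not close the gap. It serves a different purpose, and the natural reading is that the exclusion applies to it as well.

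**What to change.** Keep the exclusion as one presentation and make three changes.

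1. In SAP Section 7.2.1, report the number of excluded bleeds and of subjects contributing them, by regimen. Add a listing with the product used, the BAX326 infusions given and the recorded rating.
2. In SAP Section 7.2.1, add one FAS sensitivity table of the efficacy rating. Every bleed treated with at least one BAX326 infusion stays in the denominator, and those with another hemostatic product count as not excellent/good. Their recorded ratings appear in the listing.
3. In SAP Section 5.5, state the exclusion and its reason, for example that a rating after a second product is confounded.

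The cost is one table, one listing and a few sentences, using data that Protocol Section 11.3 already requires. The percentage may look slightly less favourable. The sensitivity figure is deliberately conservative, because it also counts adjunct-only use as not successful. If no bleed was excluded, a reported zero settles the question.

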7.2.2 Prophylaxis: Annualized Bleed Rate

The ABR will be calculated as follows:

$$\frac{\text{Number of bleeding episodes}}{\text{Observed treatment period in days}} * 365.25.$$

The ABR will be listed and summarized only for subjects who have adequate treatment time for bleeding rate assessment. For subjects on prophylaxis, a subject is considered to have an adequate treatment time for bleeding rate assessment if the observation period with BAX326 in this study within the respective treatment regimen was a minimum of 3 months (treatment period for surgery and bleeding period are not counted).

The observation period for prophylactic treatment is considered as the time between the first and the last prophylactic infusions. For transitioning subjects, infusions prior to eligibility assessment will count in case the treatment regimen is the same as the regimen the subject receives after eligibility is confirmed. The treatment period for surgery as well as the bleeding period will be excluded from the calculation of observation period in the calculation.

Additionally, the ABR will also be calculated for subjects with on-demand treatment. The observation period for on-demand treatment is considered as the time between the date of eligibility (or the date of switching to on-demand for subjects who were on prophylaxis before) and the end of observation period.

These tables will be created by treatment regimen.

ABR will be also presented by bleeding site (joint/non-joint), cause (spontaneous/injury), severity (minor, moderate, major, and life/limb-threatening), presence of target joints and FIX activity levels at screening. These subgroup analyses will be performed on the FAS only.

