#### 14.3.2 Secondary Outcome Measures

##### 14.3.2.1 Hemostatic Efficacy

The efficacy of the IP in the treatment of bleeds will be summarized. It includes the overall hemostatic efficacy rating at resolution of bleed, and the number of infusions and the total weight-adjusted dose per bleeding episode.

The annualized rate of bleeding episodes (ABR) will be calculated by treatment regimen only for subjects who have adequate treatment time for bleeding rate assessment as follows: (Number of bleeding episodes / Observed treatment period in days)\*365.25.

The observation period for prophylactic treatment will be the time between the first and the last prophylactic infusions.

Product consumption of the IP will be summarized during the study, including the average number of infusion and the average weight-adjusted consumption per months and per year, and the average weight-adjusted consumption per event (prophylactic infusion and bleeding treatment).

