5. STATISTICAL CONSIDERATIONS

Safety, efficacy, PK, HRQoL and immunogenicity data from the additional BAX326 naïve subjects (Cohort 2) will be analyzed together with the data from the previously treated subjects (Cohort 1).

The pediatric (< 12 years) and the adolescent/adult (≥ 12 years) data (i.e. age group 1) will be summarized separately and overall for all outcome measures except for analyses mentioned in section 10, section 11 and pharmacokinetic analyses (it turned out that only adults underwent an abbreviated PK study). Further analyses will occur between the age groups <6 years, ≥ 6 to <12 years, ≥ 12 to <18 and ≥ 18 (i.e. age group 2) for all outcome measures except for analyses mentioned in section 10, section 11.1 and pharmacokinetic analyses.

In case it is specified that analyses for a specific outcome measure will also be presented by treatment regimen, the summary statistics should be presented by individual treatment regimen (standard prophylaxis, modified prophylaxis, PK-tailored prophylaxis and on-demand treatment) as well as for overall prophylaxis (combined standard, modified and PK-tailored prophylaxis).

If a subject changes regimen during the course of the study, then the data from that subject will be analyzed under the initial allocated regimen until a change of regimen is recorded. Data recorded after this stage will be analyzed under the updated regimen.

In general, all efficacy, safety, PK, HRQoL and immunogenicity variables will be summarized using descriptive statistics. Continuous variables will be summarized by sample size [n], mean, standard deviation [SD], median, minimum, maximum, Q1 and Q3. Categorical variables will be summarized in frequency tables (n, frequencies, and percentages). Additional statistics which will be provided for specific endpoints will be described in the corresponding section.

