Note that the regimen, dose and/or frequency of dosing may change during the prophylaxis observation period.

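### The prophylaxis ABR denominator is a single first-to-last-infusion span with no carve-out for time on another regimen; read literally, it understates ABR for subjects who leave and return (minor)

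*SAP*

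**What the plan says.** SAP 7.2.2 and Protocol 14.3.2.1 compute ABR as the number of bleeds divided by observed days, times 365.25. Both use the same span for prophylaxis; the SAP wording is "The observation period for prophylactic treatment is considered as the time between the first and the last prophylactic infusions".

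The SAP then lists what comes out of that span: "The treatment period for surgery as well as the bleeding period will be excluded from the calculation of observation period in the calculation". Time on another regimen is not on the list.

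On reporting level, SAP 7.2.2 says "These tables will be created by treatment regimen". Under SAP 5, this means a row for each regimen plus a combined row for overall prophylaxis.

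On switching, SAP 5 keeps a subject's data under the first regimen until a change is recorded, and then: "Data recorded after this stage will be analyzed under the updated regimen".

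A subject on prophylaxis enters the ABR table only "if the observation period with BAX326 in this study within the respective treatment regimen was a minimum of 3 months".

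For on-demand treatment, SAP 7.2.2 starts the clock at eligibility, or at the switch for a subject previously on prophylaxis, and stops it at the end of the observation period. It does not define that end for someone who goes back to prophylaxis.

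**The concern.** The numerator is split whenever the regimen changes. The denominator is described as one span, and no sentence splits it. If a subject leaves and comes back, the interval away can stay in the denominator while its bleeds are counted elsewhere. Where that happens, the error in the prophylaxis ABR has only one direction: it makes the rate look lower, hence more favourable.

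Switching is foreseen. SAP 6.6 states: "Note that the regimen, dose and/or frequency of dosing may change during the prophylaxis observation period". SAP 9.1, 10.1, 10.2 and 11.2 each set up a reporting group of subjects who moved between on-demand and prophylaxis. Protocol 8.2 allows participation of up to 68 months, which leaves time for more than one change.

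Two related items hang on the same wording. An inflated span could help a subject reach the 3-month minimum. And the undefined end of the on-demand period could leave prophylaxis days in the on-demand denominator.

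**Working it through.** **No figure to reproduce.** The documents give no ABR, sample-size basis or power for this study. The only rate used below is an assumption taken from the pivotal study (Protocol 6.4.1): mean 4.20, SD 5.75, n=56. Its stated interval checks: 4.20 ± t(55) × 5.75/√56 gives 2.66 to 5.74, as printed.

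**Formula.** Let a subject spend T months on the regimen in two stretches, with g months elsewhere in between, and bleed at annual rate r while on the regimen.
- By time on regimen: ABR = r.
- By first-to-last span, with the interlude's bleeds counted elsewhere: ABR = r × T/(T+g).
- Relative fall: g/(T+g). If there were no bleeds on the regimen, both are 0.

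(g is net of any bleeding or surgery days in the interlude, which the SAP already removes.)

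**One subject in days.** Assume 12 months on, 6 months away, 12 months on, and 4 bleeds while on the regimen.
- On-regimen time: 4/730.5 × 365.25 = 2.00.
- Span: 4/(730.5 + 182.6) × 365.25 = 1.60, a fall of 20%.

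**Range over assumed T and g, at r = 4.20:**

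| T (months) | g (months) | ABR by span | Fall |
|---|---|---|---|
| 48 | 1 | 4.11 | 2.0% |
| 48 | 6 | 3.73 | 11.1% |
| 24 | 3 | 3.73 | 11.1% |
| 24 | 6 | 3.36 | 20.0% |
| 24 | 12 | 2.80 | 33.3% |
| 6 | 3 | 2.80 | 33.3% |
| 6 | 12 | 1.40 | 66.7% |

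**Group mean.** If a share f of subjects return, and all have the same on-regimen rate, the mean becomes r × [(1−f) + f × T/(T+g)]. With r = 4.20, T=24, g=6:
- f=5%: 4.20 × 0.99 = 4.16 (−1%)
- f=10%: 4.20 × 0.98 = 4.12 (−2%)
- f=20%: 4.20 × 0.96 = 4.03 (−4%)

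**Which rows are touched.**
- Overall prophylaxis: only an on-demand interlude matters. If the interlude is another prophylaxis regimen, both its bleeds and its days fall in the pooled row.
- Single-regimen rows: any interlude matters, but only if the span is read as first to last infusion on that regimen.

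**Three-month minimum, on the span reading.** Two 1-month stretches separated by 4 months span 6 months and pass, although only 2 months were on the regimen. The ABR would then be 2/6 of its on-regimen value, a fall of 67%.

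**On-demand clock.** Take prophylaxis 12 months, on-demand 6, prophylaxis 12. If the undefined end is taken as the end of the subject's follow-up, on-demand time is 6 + 12 = 18 months and the prophylaxis span is 30 months. That is 48 months of denominator from 30 months of follow-up. The on-demand ABR would be 6/18 of its on-regimen value.

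**The case against.** The best reply is that the SAP can be read so that nothing goes wrong. The span sentence does not say that it runs within a regimen, and nowhere does the SAP say that time on another regimen is counted. The 3-month sentence ties the observation period to the respective regimen, and the switching rule in SAP 5 speaks of data in general. Infusion records are data as well as bleeds. If days and bleeds are both split at the change, the bias is zero. This stands, and it means that the regimen-specific error depends on a reading.

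It does not remove the point. The regimen wording sits in the adequacy sentence, not in the definition of the period. Even carried over, it fixes the two ends of the span and does not say that an interlude between them is dropped. For the overall-prophylaxis row, the literal rule spans the on-demand interval.

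The reply is also right on scale. Protocol 8.6.3.1 prefers that the regimen be kept to the end. Newly recruited subjects cannot go on-demand. Subjects with no bleeds keep an ABR of 0 (24 of 56 in the pivotal prophylaxis group had none). Medians are reported too. ABR is a descriptive secondary outcome in an uncontrolled study, and no test rests on it.

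Three stronger conclusions are tempting and are not supported:
- That the SAP definitely puts interlude time into every regimen-specific denominator. It leaves this open.
- That even a one-way switcher has both regimens' time in each row, because any prophylactic infusion could open or close the span. The 3-month sentence and SAP 5 both point away from this.
- That the trial's reported ABR is materially flattered. The share of returners is unknown, so no such size can be stated.

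**Conclusion.** The point holds as a minor defect in a stated rule. Read literally, SAP 7.2.2 with SAP 5 gives an overall-prophylaxis ABR that is too low by g/(T+g) for a subject with bleeds who leaves prophylaxis for on-demand and returns. On a first-to-last reading within a regimen, the same applies to the regimen-specific ABR of anyone who returns to a regimen. On the on-regimen reading there is no bias, so two programmers could derive different rates from one SAP.

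For a single returning subject, falls of 11% to 33% follow from gaps of 3 to 12 months in 24 months on the regimen. For a group mean the effect is likely to be a few per cent at most under the shares tried. These sizes rest on assumed T, g and share of returners, and on equal on-regimen rates. The on-demand period has the matching gap, since a return to prophylaxis does not close it.

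**What to change.** In SAP 7.2.2:

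1. Define observation time per regimen as the sum of all periods on that regimen, less surgery and bleeding periods. Use the recorded regimen-change dates as the internal boundaries, and the first and last infusion only at the outer ends. If each stretch were instead cut at its own last infusion, the days and bleeds between two regimens would belong to neither, contrary to SAP 5.
2. Count only bleeds with onset in those periods.
3. Apply the 3-month minimum to the summed time.
4. For overall prophylaxis, sum all prophylaxis periods and leave out on-demand time.
5. End each on-demand period at the recorded return to prophylaxis.

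The cost is a few sentences and a small programming change. Protocol 8.6.3.1 already has every regimen change recorded in the eCRF, so no new data are needed. Subjects with one continuous regimen keep the same ABR. Reporting how many subjects returned to a regimen would let readers judge the size.
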